Fruits and vegetables have also been studied for their antioxidant effects due to the phenolic and prebiotic compounds inherent to the foods. The phenolic and micronutrient compounds contribute to the effectiveness of fruits and vegetables as antioxidants. A 2013 study on the effect of increasing fruit and vegetable consumption found increased levels of -tocopherol, lutein, beta carotene, beta cryptoxanthin, and ascorbic acid through diet intervention. Increasing the amount of antioxidants in the diet can combat the effects of oxidative stress which contribute to the development of chronic disease. The beneficial compounds of fruits and vegetables remain obtainable in pressed fruit/vegetable juice. A 2017 study found pure pressed fruit and vegetable juices contained the necessary polyphenols and vitamins found in whole fruits and vegetables to maintain the positive relationship between fruit/vegetable consumption and lower incidence of chronic noncommunicable disease. Similar to studies with whole fruit, participants consuming pure fruit/vegetable juices had lower levels of lipid peroxidation and higher levels of most plasma/serum antioxidant vitamins. Therefore, pressed fruit/vegetable juices are an appropriate method through which to study the effects of fruit/vegetable consumption on the development of chronic disease.

Despite the popularity of 3-day juice fast, there is little existing literature delineating the effects of the diet intervention over other fasting protocols. 3-day juice fast programs qualify as a fast under the definition of fasting due to the low caloric intake of the participant. The 3-day juice fast program we will be utilizing provides approximately 800 -900 kcal per day, 60% and 70% less than the average recommended daily intake for women and men age 19-30, respectively. The purpose of this study is to delineate the mechanism through which juice fasting interventions affect change in methylation, gut microbiome, and inflammation markers.

STUDY ENDPOINTS:

The primary endpoints of the study are changes in epigenetic markers, gut microbiota, and biomarkers of inflammation and insulin resistance that may potentially occur after juice fasting. Secondary goals of the study include providing a foundation for future studies to examine the mechanisms of the intervention and test the intervention in a larger scale.

STUDY INTERVENTIONS / INVESTIGATIONAL AGENTS:

Group 1: Juice Fasting

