In all three arms, the three-day diet intervention will be preceded and followed by three days of self-conducted elimination diet. The pre-intervention diet will encourage participants to eat a healthy, light diet for three days (basic instructions: eat only fresh raw or cooked fruits and vegetables (preferably organic), whole grains and eggs; drink 8 glasses of water a day; avoid or eliminate alcohol, caffeine, sugar, processed foods, dairy, red meat, and gluten). The post-intervention diet will instruct participants to gradually return to eating solid foods, and limit strenuous exercise (basic instructions: follow a diet similar to the pre-intervention elimination diet; day 1 after the intervention: eat fruits & green vegetables, and drink 8 glasses of water; day 2 add in: nuts, gluten-free grains like whole oats, quinoa, or brown rice; day 3 add in: organic meats, fish, & gluten-containing grains).

Biological samples and self-reported outcomes will be collected at four time points: baseline (prior to the first elimination diet period), pre-intervention (after the elimination diet and before the three-day intervention), post-intervention (after the intervention), and 14-day post-intervention. At each time point, participants will complete questionnaire on quality of life (PROMIS - Global Health Scale, which is an NIH measure on an individual's' overall physical and psychological well-being; see appendix) and collect their own saliva and stool samples. Participants will be given self-administered toolkits and be taught how to collect the samples at their first lab visit. At each of the four time points, the research assistant will coordinate the collection of cheek swabs and bloodspot samples. Stool samples will be collected using a premoistened wipe, with written instructions provided to participants, and both stool and saliva samples will be collected by the participant at home, then provided to the research assistant at their next visit.

Over the course of the study, participants will be instructed to keep a diet diary days one through nine to record their dietary intake of each day (diet diary forms with instructions attached), as well as fill out a modified version of the PROMIS Global Health Scale. During the intervention period, the research team will also contact the participants to check in with them. Participants will not need to record diet data for the fourteen day post intervention period.

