This study will not include vulnerable populations (adults unable to consent, individuals who are not yet adults, pregnant women, and prisoners).

PARTICIPANT POPULATIONS:

Number:	Category/Group:	Consented:	Enrolled:
	Special/Vulnerable	Consented or Reviewed/Collected/Screened	Number to Complete the Study or Needed to Address the Research Question
Local	Adults	30	18
Study-wide	N/A	N/A	N/A
Total:		30	18

RECRUITMENT METHODS:

Flyers will be posted on the Evanston campus of Northwestern University. Interested individuals will be directed to complete a screening questionnaire online via REDCap which will include questions about general health conditions (from SF-36) and demographics. Based on the inclusion and exclusion criteria, qualified individuals would be contacted for a phone call to gauge their interest in participating in the study. This data will not be used in the study – it will be solely for the purposes of determining eligibility, and will be housed in a separate REDCap database. During the phone conversation, detailed information will be given on what participating in the study entails, and participants will be asked at the end whether they are willing to participate. If the answer is yes, they will be invited for the initial lab visit during which hard-copy consent form will be provided.

COMPENSATION FOR PARTICIPATION IN RESEARCH ACTIVITIES

Participants will be compensated for their participation in the study. Each participant will be given a gift card for \$50 when they complete the third collection of biological samples and surveys, and \$50 when they complete the final collection of biological samples and surveys.

WITHDRAWAL OF PARTICIPANTS:

Participants will have the opportunity to voluntarily withdraw throughout the study. Involuntary withdrawals will be initiated when participants report experiencing an adverse medical event (e.g., fainting or other health effects that may be related to fasting and caloric Version #:1.4 Version Date: 05/22/2018

STU#:00206611 restriction).

Failure to collect samples for one or more time periods will be reviewed on a case-bycase basis.

RISKS TO PARTICIPANTS:

Risks to participants are expected to be minimal, particularly in light of the valuable information to be gained.

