Weight, height and waist circumference measurements: These measurements will be done in a private setting by a trained research assistant.

Psychological questionnaires: Participants will be told that they can refuse to answer questions that they feel are too personal or that they feel would be too distressing to answer.

Adverse events: Participants will be asked to report significant adverse events as soon as possible to study staff, and will be provided with a study phone number for this purpose. Study physicians will be available to study staff by pager if needed to assess possible adverse events and provide clinical input, including calling participants if indicated.

POTENTIAL BENEFITS TO PARTICIPANTS:

Participants may or may not experience health benefits from juice cleansing and/or fasting. Participants will receive juice or packaged caloric-restriction meals for the 3-day intervention. They will also be compensated for their participation in the study (up to \$100). Other possible immediate and/or direct benefits to participants and society at large include: health and lifestyle changes may occur as a result of participation; knowledge may be gained about their health and health conditions; feeling of contribution to knowledge in the health or social sciences field.

DATA AND SPECIMEN MANAGEMENT AND CONFIDENTIALITY:

Biological sample collection/storage and shipment: All biological samples that will be used for this project will be collected and then de-identified and labeled with the following information: patient ID, date of collection, time of collection, and time point (baseline, pre, post and 3 days post). All samples will be stored in a -80C freezer in the lab located at Northwestern University, Department of Medical Social Sciences, [name] until ready for transfer for laboratory analysis.

Data handling for Methylation/Microbiome Testing

One set of de-identified DNA samples of stool, bloodspot, cheek swab, and saliva will be collected in sealed plastic bags and placed with a freeze pack inside of an insulated shipping container. The container will be shipped to Northwestern University NUseq Core Facility, [name] for laboratory assays.

Data handling for Glycemic and Inflammatory Biomarker Testing

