The study poses slight risk to participants. The research team will contact each participant each day during the 3-day intervention period to check on their well-being and to monitor for adverse events relating to the diet. Possible mild side-effects include headaches, fatigue, difficulty thinking, moodiness, stomach pain and hunger pangs, and changes in bowel function or frequency of urination. For any participant feeling poorly, the research team member will encourage the participant to stay hydrated, and pass along a report immediately to the PI. The PI will be the primary individual responsible for safety monitoring. If necessary, the participant will be encouraged to cease the diet and resume their usual intake. Any significant adverse side effects including syncope (fainting) or dehydration will lead to immediate cessation of the intervention for that participant.

The research team will review cumulative data from patient feedback on a weekly basis to monitor for adverse effects. No outcomes bad enough to warrant termination of the research study are expected. However, it will be on an individual basis that this option will be considered.

PROVISIONS TO PROTECT THE PRIVACY INTERESTS OF PARTICIPANTS:

We will collect no identifying information with the data of interest to this study. All such deidentified data will be stored on a secure, password-protected computer at the Osher Center for Integrative Medicine or the Department of Preventive Medicine. Only the study research assistant and principal investigators will have access to these data. The trained research assistant will explain all study procedures in detail during the informed consent process and answer any of the participants' questions. Participants' names and mailing addresses will be provided to KitchFix or Pressed Vibrance for the purposes of food/drink delivery only. This information will not be stored with any study data.

Encrypted and computerized data of the laboratory measurement will be used. Throughout the conduct of the present study, stringent guidelines will be used to ensure privacy and confidentiality. The methylation data generated from this project will be stored without the original identifying information in the Department of Preventive Medicine at Northwestern University's Feinberg School of Medicine where all data entry and data management will be performed. Double entry with 100% verification will be used to ensure accuracy of the process.

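### Withdrawing participants from the study, rather than from the diet, after a diet-related adverse event would lose their post-diet primary-endpoint samples, mainly in the two restricted arms

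*Protocol*

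**What the plan says.** Protocol, Withdrawal of Participants: after allowing voluntary withdrawal at any point in the study, the section continues, "Involuntary withdrawals will be initiated when participants report experiencing an adverse medical event". The examples in brackets are "fainting or other health effects that may be related to fasting and caloric" restriction. The next paragraph adds: "Failure to collect samples for one or more time periods will be reviewed on a case-bycase basis".

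Protocol, Provisions to Monitor the Data to Ensure the Safety of Participants: "Any significant adverse side effects including syncope (fainting) or dehydration will lead to immediate cessation of the intervention for that participant". For a participant who merely feels unwell the response is graded: hydration, a report to the principal investigator, and then "If necessary, the participant will be encouraged to cease the diet and resume their usual intake".

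Protocol, Risks to Participants (adverse events): "Participants will be asked to report significant adverse events as soon as possible to study staff".

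Protocol, Procedures Involved: samples and questionnaires are due at baseline, pre-intervention, "post-intervention (after the intervention), and 14-day post-intervention".

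Protocol, Study Endpoints: the primary endpoints are "changes in epigenetic markers, gut microbiota, and biomarkers of inflammation and insulin resistance that may potentially occur after juice fasting".

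**The concern.** The rule ties loss of follow-up to the participant's response to the assigned diet. Someone who faints on day 2 of the juice fast would leave the study before either post-diet collection, so no change from the diet could be computed for that person. A statistical analysis plan can choose how to handle missing values, but it cannot restore a stool, saliva or blood-spot sample that nobody took. Whether to collect is a protocol decision.

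The loss is also unlikely to be even across arms. The trigger names fasting and caloric restriction, and Risks to Participants expects minor adverse effects in people on restricted intake. Two of the three arms restrict intake; juice plus usual diet does not. Those left in the restricted arms would be the people who tolerated the diet, compared with a third arm that had no such filter. If tolerance is related to the inflammatory, glycemic, methylation or microbiome outcomes, that comparison is biased.

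**Working it through.** **1. The two sections compared.**

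| | Withdrawal of Participants | Safety monitoring |
|---|---|---|
| Event | Fainting, or other effects possibly due to the diet | Syncope, dehydration, other significant effects |
| Action | Involuntary withdrawal | Stop the intervention |
| Study status afterwards | Leaves the study (natural reading) | Not stated |
| Later samples | Not provided for | Not provided for |

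The reading of withdrawal as leaving the study rests on two things: the sentence follows directly on voluntary withdrawal throughout the study, and Risks to Participants speaks of withdrawing from the study with no further obligation. The sentence on missed samples provides for review of a failure to collect. It does not tell staff to seek samples from someone who has been withdrawn.

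**2. What one withdrawal costs.** Four collections are planned, two of them after the diet. Withdrawal during the three diet days loses 2 of 4, and these are the two from which post-diet change is measured.

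**3. The protocol's own numbers.** Qualifications to Conduct Research assumes 50% ineligible or withdrawn: 18 / (1 − 0.5) = 36, as stated. Participant Populations plans 30 consented and 18 completing: 1 − 18/30 = 40% attrition. Procedures Involved expects 3 men and 3 women, hence 6 per arm, after attrition. None of these gives an adverse-event rate, and the 40% may already include some withdrawals of this kind.

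**4. Illustration of size, on assumptions only.** Assume 10 randomised per arm (30/3; the allocation ratio is not stated), k of 10 withdrawn in a restricted arm, none in juice plus usual diet, and correlation r between tolerance and outcome. In the most selective case the k least tolerant leave. The mean tolerance z-score of those remaining is then about 0.17, 0.32 and 0.46 for k = 1, 2, 3, and bias = r × that mean.

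| k | r = 0.1 | r = 0.3 | r = 0.5 |
|---|---|---|---|
| 0 | 0 | 0 | 0 |
| 1 | 0.02 SD | 0.05 SD | 0.09 SD |
| 2 | 0.03 SD | 0.10 SD | 0.16 SD |
| 3 | 0.05 SD | 0.14 SD | 0.23 SD |

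Neither k nor r comes from the protocol, and k = 0 is plausible. The model also treats the missing values as outcomes of a full diet, which early stoppers would not supply.

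**5. Why no power gain is claimed.** For a two-sample t-test at two-sided 0.05 and 80% power (my assumptions; the protocol states neither), the detectable difference is 1.80 SD at 6 v 6 and 1.71 SD at 7 v 6. If the seventh person stopped early and kept a fraction f of the diet effect, the as-randomised contrast is multiplied by 1 − (1/7)(1 − f). This is 0.952, 0.905 and 0.857 for f = 2/3, 1/3 and 0. The full-diet effect then detectable is 1.713/0.952 = 1.80, 1.713/0.905 = 1.89 and 1.713/0.857 = 2.00 SD. The gain is cancelled or outweighed.

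**The case against.** A reader might infer a flat contradiction, with one section removing the participant and the other stopping the diet alone. The text does not support that. The safety section says nothing on study status, so both rules can be applied to the same person: stop the diet now, then process the withdrawal. What remains is a poorly framed withdrawal rule, not two irreconcilable instructions. It also stands that later sampling is nowhere forbidden. Its loss follows from withdrawal with no provision to continue, and the consent pages, which could address this, are not in the text reviewed.

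A reader might also infer that any headache removes a participant. The withdrawal sentence sets no severity threshold, but the graded response in the safety section and the request to report significant events point to more serious ones. Those may be rare here. Participants are healthy, aged 18 to 35, with syncope among the exclusions and hypoglycemia and diabetes screened out, and the diet lasts three days. Withdrawals of 1 to 3 in 10 are not supported by anything in the protocol.

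The most substantial objection is that retained early stoppers have not had the three-day diet the study sets out to examine. With 1 of 10 stopping and f between 2/3 and 0, the as-randomised effect shrinks by (1/10)(1 − f), or 3.3% to 10%. On a 1.80 SD effect that is 0.06 to 0.18 SD, more than the illustrative 0.02 to 0.09 SD of bias for one withdrawal. This is a fair argument about which analysis to prefer. It is not an argument against collecting: with the samples in hand both analyses are possible, and without them only the completer analysis is.

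**Conclusion.** The point holds as a defect in the withdrawal rule that should be corrected. Followed as written, the rule loses the post-intervention and 14-day primary-endpoint samples of participants selected by their reaction to a restricted diet, and this could bias the comparison of each restricted arm with juice plus usual diet.

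The size cannot be derived from the documents. The figures of 0 to 0.23 SD are illustrations on assumed withdrawal counts and correlations under the most selective loss; the true effect may be zero or small. Even the largest is about one-eighth of the 1.80 SD detectable at 6 v 6 (0.23/1.80 = 0.13). The case for change rests on keeping the randomised arms comparable, not on power.

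A reader might extend the point to juice fast against caloric restriction. The documents do not support this: calories are matched, one arm is liquid and the other whole food, and nothing shows which is better tolerated.

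The conclusion assumes that withdrawal means leaving the study. If the investigators mean leaving the diet, the wording still needs to say so.

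**What to change.** Reword Withdrawal of Participants along these lines: an adverse event that may be related to the diet stops the diet, not study participation; the remaining scheduled samples and questionnaires, with the payments attached to them, are still sought from the participant with consent, unless a study physician advises against it. Record the date the diet stopped. Report the as-randomised comparison and, beside it, results among those who completed the diet.

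The cost is a reworded rule, one recorded date, and for each participant retained up to two more collections with their assays and gift cards (2 × $50 = $100) at visits already scheduled. Safety handling does not change, because the diet still stops as the safety section requires, and voluntary withdrawal is unaffected. The downside is that outcomes after a shortened diet dilute the as-randomised contrast, which then estimates the effect of assignment rather than of a completed three-day diet. The completer results address that question, with the caution that completers are no longer a randomised comparison.

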- 2. Subjects who, according to the investigator, can and will comply with the requirements of the protocol and are available for all scheduled visits at the investigational site.
- 3. Healthy male or female aged between 18 and 35 (included) years
- 4. $18.5 \le BMI \le 30 \text{ kg/m}^2$
- 5. Ability to give their informed consent in writing

Individuals meeting any of the following criteria may not participate in the study:

- Documented history of previous cardiovascular disease, including CHD (angina, myocardial infarction, coronary revascularization procedures or existence of abnormal Q waves in the electrocardiogram (EKG)), stroke, syncope, and clinical peripheral artery disease with symptoms of intermittent claudication.
- 2. Severe medical condition that may impair the ability of the person to participate in a nutrition intervention study (e.g. digestive disease with fat intolerance, advanced malignancy, or major neurological, psychiatric or endocrine disease including diabetes).
- 3. Daily use of any prescription or non-prescription medication that has a high likelihood of impacting systemic inflammation (e.g. non-steroidal anti inflammatories or steroids), blood sugar control (e.g. medication for diabetes) or the human microbiome (e.g. antibiotics).
- 4. Any other medical condition thought to limit survival to less than 1 year.
- 5. Known immunodeficiency disorder
- 6. Illegal drug use or chronic alcoholism or total daily alcohol intake >80 g/d.
- 7. Difficulties or major inconvenience to change dietary habits
- 8. Impossibility to follow an elimination or juice fast diet, for religious reasons or due to the presence of disorders of chewing or swallowing (e.g., difficulties to consume nuts)
- 9. A low predicted likelihood to change dietary habits according to the Prochaska and DiClemente stages of change model (Nigg, 1999).
- 10. History of food allergy with hypersensitivity to any of the components of the juice or diet
- 11. Patients with an acute infection or inflammation (e.g., pneumonia) are allowed to participate in the study 3 months after the resolution of their condition.
- 12. Dietary restrictions due to medical (including allergies), religious, or other concerns

13. Any diagnosis of allergic rhinitis, eczema, asthma, or inflammatory bowel disease (e.g. ulcerative colitis or Crohn's) from a health professional

VULNERABLE POPULATIONS:

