Diet intervention: Fasting and juice cleanse diets over short periods are generally safe, but may cause some minor discomfort during the study period. For those on restricted intake diets, several minor adverse effects may occur and include constipation, headache, muscle cramps, diarrhea, general weakness, and rash. Most of these are short-lived, and are generally alleviated by adequate fluid intake and other minor diet modifications. The restricted diet may lead to decreases in glucose levels; this risk will be mitigated by screening participants for the exclusion criteria of diabetes, hypoglycemia, steroid-dependent diseases and use of medications that impact on blood sugar such as sulfonylureas and insulin.

Blood Spot: There is a small risk that the puncture associated with the blood spot may cause bruising or infection at the site of the needle insertion.

Weight, height and waist circumference measurements: There is no physical risk involved in measuring weight, height, and waist circumference but there is a risk of embarrassment or discomfort at being measured in one's underclothes.

Behavioral and psychological questionnaires: These carry a minimal risk for emotional discomfort and stress.

Participants will be fully informed of all of these risks during the informed consent process and be given the opportunity to withdraw from the study at any time without any further obligation. No data will be collected until informed consent has been obtained. We expect all of these risks to be temporary, and to quickly subside after the study is concluded.

Efforts to minimize risk are as follows:

Dietary intervention: Participants will be instructed to speak to the research associate or principal investigator if they experience discomfort, such as constipation, diarrhea, weakness, muscle cramps, or dizziness. There is instruction provided with the juice cleanse on how to address any potential side effects stemming from the diet. Participants will be told that their participation is voluntary and they can choose to withdraw from the study at any time without any further obligation.

Blood spot: Bloodspot collection will be done as professionally and comfortably as possible. Blood is collected for the in-person assessments in a sterile manner to reduce the threat of infection. Likewise, pressure is applied to the puncture site to prevent hemorrhage and ecchymosis.

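### The risk section relies on hypoglycemia and steroid-dependent disease being exclusion criteria, but the exclusion list omits the first and covers the second only indirectly, so the stated glucose safeguard is incomplete

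*Protocol*

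**What the plan says.** Four sections of the protocol bear on who is kept out of the study.

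- *Risks to Participants* (diet intervention) names the hazard and the safeguard: "The restricted diet may lead to decreases in glucose levels; this risk will be mitigated by screening participants". It then lists what the screening covers: "screening participants for the exclusion criteria of diabetes, hypoglycemia, steroid-dependent diseases", together with blood-sugar medication, giving sulfonylureas and insulin as examples. These are presented as exclusion criteria that already exist.
- *Inclusion and Exclusion Criteria* has 13 numbered exclusions. Item 2 excludes severe conditions, with "major neurological, psychiatric or endocrine disease including diabetes" among its examples. Item 3 excludes daily use of medication likely to affect inflammation, blood sugar or the microbiome ("e.g. non-steroidal anti inflammatories or steroids), blood sugar control (e.g. medication for diabetes"). Inclusion 1 asks the investigator to judge the person healthy from the medical history and the screening questionnaire. Inclusion 3 reads "Healthy male or female aged between 18 and 35 (included) years".
- *Vulnerable Populations* says that the study will not include "adults unable to consent, individuals who are not yet adults, pregnant women, and prisoners".
- *Recruitment Methods* says how the criteria are applied: "Based on the inclusion and exclusion criteria, qualified individuals would be contacted for a phone call". It describes the online screener as including general health questions from the SF-36 and demographics.

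**The concern.** The risk section justifies a restricted diet partly by pointing to exclusions. If a condition named there is not in the list that staff apply, a person with that condition can meet every listed criterion and be enrolled, although the safety text says that such a person is kept out.

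This matters because screening is the only safeguard in the protocol aimed specifically at low glucose. The other protections are general. The blood-spot markers named under *Biomarker Testing* are C-reactive protein, interleukin-6, insulin and leptin, so glucose is not among them.

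Eligibility belongs in the protocol and is not something a statistical analysis plan would normally supply, so the missing SAP does not explain the gap.

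**Working it through.** The protocol gives no figure to reproduce on this point. The check sets each condition claimed elsewhere in the protocol against inclusion criteria 1–5 and exclusion criteria 1–13.

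| Condition | Where it is said to be kept out | In the numbered list? |
|---|---|---|
| Diabetes | Risks to Participants | Yes, by name, in exclusion 2 |
| Blood-sugar medication | Risks to Participants | Yes, in exclusion 3, limited to daily use |
| Steroid-dependent disease | Risks to Participants | Not by name; reached through daily steroid use (exclusion 3) and major endocrine disease (exclusion 2) |
| Hypoglycemia | Risks to Participants | No |
| Pregnancy | Vulnerable Populations | No |

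**Tally for the risk section.** Of the four conditions it calls exclusion criteria, 2 are listed, 1 is covered indirectly and 1 is absent (2 + 1 + 1 = 4).

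**Can another item stand in for hypoglycemia?** Exclusion 2 needs a severe condition or a major endocrine disease, and a history of hypoglycemia need be neither. Exclusion 3 concerns medicines, not conditions. Exclusion 1 names syncope, but only as an event in the person's history. Inclusion 1 could catch a case, but it rests on judgement and names no condition. No listed item requires the exclusion that the risk section claims.

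**Pregnancy.** The protocol plans up to 15 women among up to 30 participants, aged 18 to 35. The statement that pregnant women are not included stands outside the numbered list. The protocol describes no screening question or test that would give effect to it.

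**Number on the restricted diets.** Two of the three arms, juice fasting and caloric restriction, are assigned 800–900 kcal per day. With equal allocation of the maximum enrolment this is 30 × 2/3 = 20 people. Among the expected completers (3 men and 3 women per arm, 18 in all) it is 18 × 2/3 = 12. These numbers count everyone to whom the safeguard applies. They do not estimate how many would be wrongly admitted, and the protocol gives no figure from which to derive that.

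**The case against.** The strongest reply is that the list is not the whole screen.

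- **Investigator judgement.** The investigator must consider each person healthy on the medical history, and a phone call and a lab visit follow the online form. This stands as a backstop. It is discretionary, however, and does not turn hypoglycemia into the criterion that the risk section says it is.
- **The screener is not reproduced.** Its description need not be exhaustive, and the risk section itself commits to screening for these conditions. It is therefore not shown that the screener omits them. What is shown is that the list said to decide contact does not require them.
- **Steroids.** Excluding daily steroid use covers most of what steroid-dependent disease would mean in practice. This largely stands; what remains is mainly a difference in naming.
- **Pregnancy.** Non-inclusion is an explicit protocol statement, and the pregnant-women box in the study summary is unticked. Nothing in the criteria contradicts it. This also stands, which is why pregnancy is only a secondary point here: a stated exclusion without a matching list item or check.
- **Other safeguards.** Participants are contacted on each intervention day, feeling poorly is reported to the principal investigator, fainting or dehydration ends the intervention, and study physicians can be paged. These are real protections, but they act after symptoms appear, whereas the claim at issue is about prevention at entry.

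A reader might go further and infer that the glucose mitigation does not exist, or that the gap alters the glycemic and microbiome results. The documents support neither. Two of the four conditions are listed outright and a third is largely covered. Nothing in the protocol allows an effect on outcome data to be sized, and in healthy adults aged 18 to 35 few people are likely to be affected.

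**Conclusion.** The point holds in a limited form. The risk section names hypoglycemia as an exclusion criterion and the list has no such criterion. It also names steroid-dependent disease, which the list reaches only through daily steroid use and major endocrine disease. With diabetes and daily blood-sugar medication listed, the stated mitigation is incomplete, not absent. The secondary gap is that the non-inclusion of pregnant women has no counterpart in the list and no described check.

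The conclusion assumes that staff apply the numbered list as written, as *Recruitment Methods* says. If the unseen screener already asks about these conditions, the practical risk is smaller, but the sections still disagree. The defect is one of consistency in the safety and eligibility text. No endpoint, analysis or sample-size figure depends on it. It should still be corrected, because it concerns a safeguard that the protocol claims and that its own list does not fully deliver.

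**What to change.** Reconcile *Inclusion and Exclusion Criteria*, *Vulnerable Populations*, *Recruitment Methods* and *Risks to Participants* so that there is one eligibility list, and make the screening questions match it item by item. Every condition that the risk section says is screened out should then be in the list and be asked about. The statement on pregnant women should either appear in that list or be tied to a described check.

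If the investigators do not intend to exclude one of these conditions, the alternative is to restate the mitigation claim so that it names only what is excluded. Which clinical criterion is right is their decision.

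The cost is a few lines of protocol text and a few screener questions, with possibly a few extra screen failures. Nothing in the design or the analysis has to change.
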